5.2. Exclusion Criteria

Participants are excluded from the study if any of the following criteria apply:

Medical Conditions

13. Have had an allogeneic bone marrow or solid organ transplant.
14. Have received recent (within 4 weeks prior to Cycle 1 Day 1) live vaccination. Seasonal flu and COVID vaccines that do not contain a live virus are permitted.
15. Patients with psychiatric illness/social situation that, in the opinion of the investigator, could cause unacceptable safety risks or compromise compliance with the protocol.
16. Exclusion Criterion 16 has been deleted.
17. Have a known intolerance or hypersensitivity (such as urticaria, allergic reaction including anaphylaxis, toxic necrolysis, and Stevens-Johnson syndrome) to any of the study treatments or its components relevant to the study part that is currently enrolling or a known hypersensitivity to dacarbazine
18. Diagnosed and/or treated additional malignancy within 3 years prior to enrollment that, in the judgment of the investigator and Lilly, may affect the interpretation of results, with the exception of curatively treated basal cell carcinoma of the skin, squamous cell carcinoma of the skin, and/or curatively resected *in situ* cervical and/or breast cancers.
19. Are pregnant or breastfeeding.
20. The patient has active systemic infections (e.g. bacterial, fungal, or viral infection requiring IV therapy). Individuals with stable HIV, Hepatitis B, or C for whom exposure to the investigational treatment is not expected to exacerbate their current disease may be considered eligible. Screening is not required for enrollment.
21. The patient has serious and/or uncontrolled preexisting medical condition(s) that, in the judgment of the investigator, would preclude participation in this study (such as interstitial lung disease, severe dyspnea at rest or requiring oxygen therapy, history of major surgical resection involving the stomach or small bowel, or preexisting Crohn's disease or ulcerative colitis or a preexisting chronic condition resulting in clinically significant diarrhea).
26. Patients with a bowel obstruction will be excluded from Parts A and C of this study.

Prior/Concomitant Therapy

22. Patients treated with drugs known to be strong inhibitors or inducers of isoenzyme cytochrome P450 (CYP)3A or strong inhibitors of uridine diphosphate-glucuronosyl

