transferase 1A1 (UGT1A1) if the treatment cannot be discontinued or switched to a different medication at least 5 half-lives prior to starting study drug.

23. Have received any prior CDK4 & 6 inhibitor.
30. Part C only, have received prior systemic therapy for relapsed/refractory neuroblastoma.
31. Patients with CNS disease are eligible if seizures and other neurological symptoms have been stable for 7 days. However, patients must not have received enzyme-inducing anticonvulsants, such as phenytoin, phenobarbital, valproic acid, or carbamazepine for at least 7 days prior to starting study drug. Non-enzyme-inducing anticonvulsants, such as gabapentin or levetiracetam, are acceptable.
32. Part C only, have received prior anti-GD2 therapy during induction phase

Prior/Concurrent Clinical Study Experience

24. Are currently enrolled in any other clinical study involving an investigational product or non-approved use of a drug or device (other than the study drug used in this study) or any other type of medical research judged not to be scientifically or medically compatible with this study
25. Have participated, within the last 30 days, in a clinical study involving an investigational product. If the previous product has a long half-life, 5 half-lives or 30 days, whichever is longer, should have passed. Exceptions will be considered on a case-by-case basis by the Lilly CRP/CRS.

Genetic Alterations

27. Exclusion Criterion 27 has been deleted.

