6.5. Concomitant Therapy

With the exceptions listed in the sections below, no other chemotherapy, investigational medications, other anticancer therapy, immunotherapy, hormonal cancer therapy, herbal supplements and/or herbal drugs intended to treat cancer, radiation, or surgery for cancer will be permitted while patients are on study treatment. Palliative radiation therapy will be permitted as detailed in Section 6.5.1.

Because of a potential impact on antibody-dependent cellular cytotoxicity, any treatment with immunosuppressive activity and immunoglobulins should not be administered within 21 days

prior to Cycle 1 and for 1 week after final dinutuximab infusion. However, these medications may be allowed if medically needed to treat acute, potentially life-threatening events.

Any medication or vaccine (including over-the-counter or prescription medicines, vitamins, and/or herbal supplements) that the participant is receiving at the time of enrollment or receives during the study must be recorded along with:

- Reason for use
- Dates of administration including start and end dates

Abemaciclib is extensively metabolized through oxidation by CYP3A. In clinical drug interaction studies, coadministration of clarithromycin, a strong CYP3A inhibitor, increased exposure (area under the curve [AUC]) to abemaciclib by 3.4-fold (Study I3Y-MC-JPBE) and coadministration of rifampin, a strong CYP3A inducer, decreased exposure to abemaciclib by 95% (Study I3Y-MC-JPBF). Therefore, grapefruit or grapefruit juice, cannabis, cannabis products, and other strong inhibitors of CYP3A (see Section 10.6, Appendix 6) should not be taken during Cycle 1. Beyond Cycle 1, grapefruit or grapefruit juice, cannabis, cannabis products, as well as inducers and strong or moderate inhibitors of CYP3A should be substituted or avoided if possible (see Section 10.6, Appendix 6). The information in Appendix 6 is provided for guidance to investigators and does not preclude the use of these medications if clinically indicated.

All patients may receive supportive therapy with dexamethasone, preferably ≤ 7 days, if clinically indicated. Patients requiring more than 7 days of dexamethasone therapy will not incur a protocol deviation.

Abemaciclib can be coadministered with drugs that are substrates of CYP enzymes.

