6.5.3.6. Hyponatremia (\geq Grade 3; Na < 130 mEq/L)

- Switch hypotonic fluids to isotonic fluids as compatibilities allow
- Do not administer oral free water
- Correct fluid losses caused by diarrhea
- Use 3% saline only if:
 - Hyponatremia leads to seizure
 - Sodium level decreases by > 10 points in ≤ 6 hours
 - Sodium level < 117 mEq/L
- If Grade 4 hyponatremia persists despite optimal fluid management, do not administer dinutuximab during the rest of the cycle. Monitor sodium levels closely in the subsequent cycle
- If Grade 4 hyponatremia recurs in the subsequent cycle despite optimal fluid management, permanently discontinue all study drugs.

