10.6. Appendix 6: Inducers and Strong Inhibitors of CYP3A4

Note: The information in this table is provided for guidance to investigators. This list is not intended to be exhaustive, but with available information continually evolving, the status of every relevant drug cannot be guaranteed. Please consult with the medical monitor in case of any doubt about a potential drug-drug interaction.

Strong Inducers of CYP3A4	Special Status
Aminoglutethimide	Very limited use. Possibly available in Egypt, Lithuania
Apalutamide	
Carbamazepine (daily dose exceeding 600 mg)	
Enzalutamide	
Fosphenytoin (see also phenytoin)	
Ivosidenib	
Lumacaftor	
Mitotane	
Phenobarbital	
Phenytoin	
Rifabutin	
Rifampicin (rifampin)	
Rifapentine	
St John's wort	Supplement or food/drink

Moderate Inducers of CYP3A4	
Bosentan	
Carbamazepine (daily dose 600 mg or lower)	
Cenobamate	
Dabrafenib	
Danshen (Salvia miltiorrhiza)	Supplement or food/drink
Efavirenz	
Elagolix	
Encorafenib	Probable moderate inducer based on observed autoinduction
Etravirine	
Genistein	Supplement or food/drink
Lopinavir (alone)	
Lorlatinib	
Modafinil	
Nafcillin (intravenous)	Very limited use; Available in US
Pentobarbital	Very limited use
Primidone	
Sotorasib	
Thioridazine	Very limited use; available in US; importable into UK
Tocilizumab (atlizumab)	Non-traditional mechanism: reverses the IL-6 mediated suppression of CYP3A activity in patients with rheumatoid arthritis

Strong Inhibitors of CYP3A4	
Atazanavir and cobicistat	
Boceprevir	
Ceritinib	

Clarithromycin	
Cobicistat (see atazanavir and cobicistat)	
Conivaptan	
Danoprevir and ritonavir	
Elvitegravir and ritonavir	
Fosamprenavir and ritonavir	
Grapefruit juice	Supplement or food/drink
Idelalisib	
Indinavir and ritonavir	
Itraconazole	
Josamycin	Outside US
Ketoconazole	Very limited use
Lonafarnib	
Lopinavir and ritonavir	
Mifepristone	Very limited use; Cushing's disease in US
Nefazodone	Very limited use; Available in US
Nelfinavir	
Nirmatrelvir and ritonavir	
Posaconazole	
Ribociclib	
Ritonavir	
Saquinavir and ritonavir	
Telithromycin	
Tipranavir and ritonavir	
Tucatinib	
Viekirax (paritaprevir and ritonavir and ombitasvir and/or dasabuvir)	Outside of US
Voriconazole	

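### Strong CYP3A inducers are not restricted in Cycle 1, and the DLT-evaluability rules do not remove a DLT-free patient who starts one

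*Protocol*

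**What the plan says.** Protocol Section 6.5 reports two interaction results for abemaciclib. A strong CYP3A inhibitor (clarithromycin) raised AUC 3.4-fold, and rifampin, "a strong CYP3A inducer, decreased exposure to abemaciclib by 95" percent. The instruction drawn from these results has two steps:

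- **Cycle 1:** grapefruit, cannabis products and "other strong inhibitors of CYP3A (see Section 10.6, Appendix 6) should not be taken during Cycle 1". Inducers are not named.
- **Beyond Cycle 1:** the same items "as well as inducers and strong or moderate inhibitors of CYP3A should be substituted or avoided if possible". This is where inducers first appear.

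The section adds that the Appendix 6 list "does not preclude the use of these medications if clinically indicated". That appendix names phenytoin, fosphenytoin and phenobarbital among the strong inducers.

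Two entry criteria in Section 5.2 deal with inducers. Exclusion 22 covers "Patients treated with drugs known to be strong inhibitors or inducers of isoenzyme cytochrome P450 (CYP)3A" when these cannot be stopped or switched 5 half-lives before study drug. Exclusion 31 says that patients with CNS disease "must not have received enzyme-inducing anticonvulsants, such as phenytoin, phenobarbital, valproic acid, or carbamazepine for at least 7 days prior to starting study drug", and names gabapentin and levetiracetam as acceptable.

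DLT evaluability is set out in protocol 4.1.1 and 9.3 and SAP 6.1.1 and 7.1.1. It turns on completing Cycle 1, compliance and receipt of at least 75% of planned doses, or on a DLT or drug-related toxicity. Section 6.4 defines compliance by doses taken.

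**The concern.** Section 6.5 gives evidence in both directions, but its Cycle 1 instruction follows from only one of them. As written, the plan is looser on inducers inside the DLT window than after it.

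The second gap is independent of the first. Nothing in the evaluability rules looks at interacting drugs. A patient who takes every abemaciclib dose at greatly reduced exposure, and has no DLT, enters the 3+3 count as a clean observation at the nominal dose. The error runs one way, towards clearing a dose that would not otherwise clear.

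DLTs are a primary endpoint in every part. PK is too, in Part C for Stage 1 only. The Cycle 1 Day 15 sample from such a patient would also pull down a small cohort's summary.

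**Working it through.** **Does any other rule close the gap?**

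| Provision | Acts during Cycle 1? | Removes the patient from the DLT count? |
|---|---|---|
| Exclusions 22 and 31 | No, before first dose only | No |
| Section 5.3 | Yes, grapefruit only | No |
| Section 6.5, Cycle 1 sentence | Yes, but inducers not named | No |
| Appendix 6 | Guidance only | No |
| Protocol 4.1.1, 9.3; SAP 6.1.1, 7.1.1 | Yes | No, the tests are completion, compliance and doses taken |

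None does.

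**Exposure against the plan's 75% test.** The 95% figure is a cited result and cannot be re-derived from the documents. Assume that it applies at once and in full:

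- Day 8 start: 7/21 + (14/21)(0.05) = 0.37 of planned Cycle 1 parent-drug exposure.
- Day 15 start: 14/21 + (7/21)(0.05) = 0.68.

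Both are below 0.75. The rule counts doses, not exposure, so this is an analogy only.

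**Effect on 3+3.** A dose clears on 0/3, or on 1/3 followed by 0/3. With true DLT rate p:

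P(clear) = (1−p)³ + 3p(1−p)⁵. At p = 1/3 this is 0.2963 + 0.1317 = **0.428**.

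With one of the first three patients at a lower risk q:

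P(clear) = (1−p)²(1−q) + [2p(1−p)(1−q) + (1−p)²q](1−p)³.

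At p = 1/3 the bracket equals 4/9 for every q, so P(clear) = 0.4444(1−q) + 0.1317.

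For q, assume a constant DLT hazard over 21 days and immediate induction from the start day s.

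*No residual risk from the other drugs,* q = p(s−1)/21:
- Day 8: q = 0.111, P = 0.3951 + 0.1317 = **0.53**.
- Day 15: q = 0.222, P = 0.3457 + 0.1317 = **0.48**.

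*Half the risk from the other drugs (assumed),* Day 8:
- q = (1/3)(1/2 + 1/2 × 1/3) = 0.222, P = **about 0.48**.

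**Average over patients.** The documents give no frequency of new starts. With an assumed chance r of 2% to 5% per patient, the effective risk is p − r(p−q). With no residual risk, clearance is 0.437 to 0.450 for Day 8 starts and 0.432 to 0.439 for Day 15 starts, against 0.428. The Day 8 case with half the risk from other drugs has the same q as the Day 15 case, so it also gives 0.432 to 0.439.

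**PK.** If the 95% fall applied in full to one patient's Cycle 1 Day 15 sample and levels were otherwise equal, the cohort mean for parent drug would fall by 0.95/3 = 32% (n = 3) or 0.95/6 = 16% (n = 6). For an inducer half as strong, the falls are 16% and 8%. The effect on the active metabolites M2 and M20 is not given.

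**The case against.** The strongest reply is that the asymmetry may be deliberate. The Cycle 1 rule for UGT1A1 in the same section also names inhibitors only, which fits a rule aimed at over-exposure. An induced patient would also be visible: concomitant drugs are recorded with dates, abemaciclib is sampled on Cycle 1 Day 15, dose decisions follow investigator–sponsor discussion, and the RP2D uses PK. Expansion cohorts, the review after every third expansion patient and Part C Rules A and B are further checks. All of this stands and keeps the expected effect small. None of it restricts inducers in Cycle 1 or takes the patient out of the DLT count.

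Three stronger readings are tempting but not supported:

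- **That the omission in 6.5 makes the patient evaluable.** It does not. A patient who took a strong inhibitor against the Cycle 1 sentence would also stay evaluable. The two gaps are separate.
- **That editing 6.5 alone is enough.** An anticonvulsant started for a seizure is a clinically indicated use, which the section allows. The patient would still be counted.
- **That Part C supplies a route, because Section 6.5.3.6 provides for the case where "Hyponatremia leads to seizure".** The response given there is 3% saline. Under protocol 4.1.3 a Grade 3 or higher electrolyte abnormality escapes DLT status only if it is not clinically complicated. Hyponatremia with a seizure would ordinarily be a DLT if judged at least possibly related, so that patient is not DLT-free.

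**Conclusion.** The gap is real and its expected effect is small. Strong inducers are unrestricted by the Cycle 1 sentence, and a DLT-free patient who starts one counts at the nominal dose. The most plausible case is a CNS-tumour patient in Part B. Part A's MTD is already set at 55 mg/m², and nothing in the documents shows that it was affected.

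The shift from 0.428 to at most 0.53 or 0.48 is conditional on one of the first three patients being affected. It needs immediate full induction, a constant DLT hazard and no DLT risk from temozolomide or the other partner drugs. The last assumption is generous, because 4.1.3 counts events related to the combination. The 95% figure is for rifampin, and weaker inducers would do less. Confidence is high in the textual gap and low in any particular size of effect. The case for acting is that the bias runs in the unsafe direction and the correction is nearly free.

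**What to change.** Make both changes together.

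1. **Section 6.5:** extend the Cycle 1 sentence to strong inhibitors *and strong inducers* of CYP3A. Keep the allowance for clinically indicated use, and point to the non-inducing anticonvulsants named in exclusion 31.
2. **Protocol 4.1.1 and 9.3, SAP 6.1.1 and 7.1.1:** add one sentence. A DLT-free patient who took a strong CYP3A inducer for a substantial part of Cycle 1 is DLT non-evaluable and may be replaced; a patient with a DLT stays evaluable. Clinical pharmacology should set the threshold in advance.

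Flag PK samples taken during inducer use, in the dose-group summaries or in the separate PK analysis plan that SAP 7.4.5 allows for.

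The cost is a phrase, a sentence and a data flag. Start and end dates of concomitant drugs are already collected. The downside is a rare replacement patient. The benefit is limited to whatever Part B and Part C Stage 1 enrolment remains.

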6.5.1. Palliative Medicine and Supportive Care

All concomitant medications should be recorded throughout the patient's participation in the study.

Palliative Medicine

- Palliative radiation therapy of ≤14 days is permitted after Cycle 6 and after discussion with and agreement of the Lilly CRP/CRS for irradiating small areas of painful metastases that cannot be managed adequately using systemic or local analgesics. Such areas must not be an identified target lesion and must not constitute progressive disease or meet RECIST criteria for progressive disease. Abemaciclib should be suspended during the palliative radiotherapy period and until complete recovery from acute reactions and potential gastrointestinal toxicities. Any symptomatic deterioration or clinical disease progression requiring, in the opinion of the investigator, other forms of specific anti-tumor systemic therapy, will be cause for discontinuation of study therapy.

Supportive Care

Patients should receive full supportive care.

- The use of anti-diarrheal (i.e. loperamide) medication is strongly recommended. See Section [6.5.2](#) for details.
- In Parts A and B, the use of G-CSF is permitted for all cycles, including Cycle 1, at the discretion of the investigator based on American Society of Clinical Oncology (ASCO) (Smith et al. 2015) and European Society for Medical Oncology (Crawford et al. 2010) guidelines. Administration of G-CSF should be considered alongside study treatment for those patients at high risk of severe neutropenia (e.g. previously treated with chemotherapy or radiation). G-CSF is not allowed in Part C.
- Erythropoietin, thrombopoietic growth factors, packed red blood cell transfusions, and other blood products may be used according to ASCO guidelines (Rizzo et al. 2008) at the investigator's discretion.
- Prophylactic antibiotic treatment should be consistent with ASCO guidelines (Lehrnbecher et al. 2017).
- *Pneumocystis jirovecii* pneumonia may occur in participants receiving irinotecan and temozolomide. PCP prophylaxis is encouraged.
- Refer to temozolomide and irinotecan labels for recommendations on prophylactic supportive care.

6.5.2. Supportive Management for Diarrhea

Diarrhea is an overlapping toxicity of abemaciclib, irinotecan, and dinutuximab. It may be difficult to discern the difference between causes of diarrhea. Investigators should attempt to

determine to which study drug the diarrhea is likely attributed using the descriptions below. Patients should receive diarrhea management instructions and maximal supportive care. Loperamide is recommended.

See Section [6.6.1.1](#) for diarrhea-related dose modifications. For patients in Part C, see Section [6.5.3.2](#) for suggested premedication to prevent diarrhea.

Guidance for diarrhea attributed to irinotecan:

Early diarrhea (onset during or shortly after infusion) is usually transient and infrequently severe. It may be accompanied by cholinergic symptoms of rhinitis, increased salivation, miosis, lacrimation, diaphoresis, flushing, and intestinal hyperperistalsis that can cause abdominal cramping. Bradycardia may occur. Early diarrhea and other cholinergic symptoms may be prevented and treated. Consider prophylactic or therapeutic administration of atropine (according to label or institutional practice) unless clinically contraindicated.

Late diarrhea (onset more than 24 hours after administration) can be life-threatening since it may be prolonged, lead to dehydration, electrolyte imbalance, or sepsis, and can be complicated by colitis, ulceration, bleeding, ileus, obstruction, and infection. Cases of megacolon and intestinal perforation have been reported. Patients should have loperamide available prior to first irinotecan infusion. Begin loperamide at the first episode of poorly formed, loose, or increased frequency of stool. Monitor and replace fluid and electrolytes. Patients should be followed closely.

Prophylactic or concomitant use of antibiotics, such as cefixime, can be used at the investigator's discretion (Wagner et al. 2008).

Refer to prescribing information for additional management of diarrhea attributed to irinotecan.

Guidance for diarrhea attributed to abemaciclib:

Diarrhea was the most frequently reported treatment-emergent adverse event (TEAE) with abemaciclib in adult Phase 3 registration studies (MONARCH 2 [Sledge et al. 2017]; MONARCH 3 [Goetz et al. 2017; Johnston et al. 2019]). Characteristics of abemaciclib diarrhea from these studies include:

- Predominantly of low severity (Grade 1 or 2) with no Grade 4 or 5 diarrhea observed.
- Incidence was greatest during the first month of abemaciclib treatment.
- The median time to onset of the first diarrhea event was 6 to 8 days, and the median duration of diarrhea for Grade 2 was 9 to 11 days and Grade 3 was 6 to 8 days (Abemaciclib US Package Insert 2019).
- Generally manageable with standard anti-diarrheal agents and dose adjustment.

Initiate supportive measures as early as possible. Supportive measures include:

- Anti-diarrheal medication (e.g. loperamide) initiation at the first sign of loose stools.
- Patient/caregiver should notify the investigator for further instructions.
- Patients should be encouraged to drink sufficient fluids.
- Site personnel should assess response within 24 hours.
- Modify treatment as outlined in Section [6.6](#) (Dose Modification).
- Adjust doses as outlined in Section [6.6.1.1](#).

If severe, measure absolute neutrophil counts, body temperature, and monitor for signs of bacterial infection. If associated with fever or severe neutropenia, begin broad-spectrum antibiotics per institutional guidelines.

Patients with severe diarrhea or any diarrhea associated with nausea or vomiting should be carefully monitored and given IV hydration and electrolyte replacement. Hospitalization should be considered.

6.5.3. Supportive Management of Anticipated Dinutuximab-Associated Toxicities (Part C Only)

Side effects during dinutuximab infusion should be anticipated and will frequently occur even with use of pretreatment medications. The need to slow, pause, or discontinue infusion should be anticipated and is not unexpected. Refer to Section [6.6.1.3](#) for dose modifications of dinutuximab.

6.5.3.1. Hypotension (Without Evidence of Allergic Reaction)

Severe Hypotension is defined as:

- Symptomatic decrease in blood pressure and/or
- Age 1-12 years: SBP <70 mmHg
- Age >12 years: SBP <80 mmHg
- Either SBP or DBP decrease by more than 15% from baseline.

If severe, accompanied by poor perfusion, end organ dysfunction, or acidemia, stop infusion and initiate resuscitation efforts.

Moderate Hypotension is defined as hypotension with normal perfusion, absence of end organ dysfunction, and without acidemia

For moderate hypotension:

- Pause dinutuximab infusion
- Give 20 mL/kg normal saline bolus
- Stop or adjust narcotic and sedating H1 blocker infusions
- Consider Trendelenberg position.

For moderate hypotension that persists despite the measures above:

- Reassess perfusion and end organ function and initiate standard resuscitation efforts
- Repeat normal saline bolus
- Consider albumin infusion if albumin level is <3 gm/dL
- Consider PRBC transfusion if Hgb is <10 gm/dL
- Consider transfer to intensive care unit.

If hypotension persists following 2 fluid boluses, give additional boluses and initiate pressors. Note that epinephrine is preferred over dopamine based on its desired vasoconstrictive properties.

Resumption of dinutuximab infusion after hypotension

For hypotension that resolves promptly and completely with limited resuscitation, dinutuximab may be resumed at 50% infusion rate. If >20 hours have elapsed since initiation of dinutuximab infusion, then do not resume that day's dose.

If same-day infusion is resumed and if blood pressures are stable for 2 hours, the infusion rate may be increased to the maximum rate for remainder of that day and subsequent days.

If hypotension recurs at a reduced same-day infusion rate, stop the infusion and repeat the supportive care measures described above. Do not administer any additional dinutuximab on that day. The following day, ensure that the patient is volume replete and begin infusion at 50% rate.

If blood pressure is stable for 2 hours at a reduced rate, the infusion can be increased to maximum rate and, if tolerated, subsequent infusion days may begin at maximum starting rate.

If blood pressure only remains stable at the 50% infusion rate, then all subsequent infusions should be initiated at the 50% infusion rate without attempts to increase.

If >60 mL/kg fluid boluses were required at maximal dinutuximab rate, but the 50% infusion rate was tolerated, then all remaining days should be administered at the 50% reduced infusion rate without attempts to increase.

If pressors were required but then were able to be discontinued and the patient's blood pressure remained stable for ≥ 6 hours following discontinuation, the next day's dinutuximab infusion may resume at 50%.

Patients who require pressor support for ≥ 24 hours or more than once must permanently discontinue all study drugs.

